Nurse training: OSUWMC MICU nurses have significant experience with CGM use in an extremely ill cohort of COVID-19 patients. Each nurse in the MICU receives training on CGM set-up, insertion, pairing, and CGM glucose monitoring features as part of their annual critical care competencies. OSUWMC MICU nurses are trained and experienced in using POC glucose measurement to validate the CGM system, however the protocol at use in this study differs somewhat from the COVID-19 protocol currently at use in the MICU. Given that, nurses will receive training on distinctions between the two protocols including changes to the frequency of POC testing, the addition of clinical status events that would warrant more frequent POC testing and validation (Q1 or Q2 hours depending on number of events present for a duration of 6 hours). New criteria to stop clinical use (i.e., no use of CGM for glucose monitoring, no use of CGM for insulin titration) will be reviewed in detail with nursing along with plans for the sensor to remain in place only for data collection. Nursing trainings will be conducted by PI ([name]), Co-I ([name]), and study coordinator during staff meetings and nursing huddles conducted on all shifts. All nurses will receive training on the new protocol prior to patient recruitment. The study protocol, along with currently available training materials, will be kept at the bedside of all patient participants.

Staggered enrollment and initial pilot: We will stagger enrollment with just 20 patient participants over a 4-week period (target 5 participants/week with a respite between enrollment to allow analysis of safety and fidelity data prior to the next round. A robust analysis would be conducted after this first “pilot” round of enrollment. Accuracy analysis would include MARD and Clark Error Grid. A full assessment of protocol adherence and evaluate adherence to standard insulin dosing guidelines will be completed. The pilot analysis will include evaluation of

benchmarks for accuracy, safety, and adverse event monitoring with benchmarks that must be met prior to subsequent enrollment. Pilot benchmarks for study continuation are as follows:

- Successful initial validation criteria within 24 hours in 80% of participants (16/20)
- Clark error grid analysis demonstrating >95% points in zone A (within 20% of reference glucose value) or zone B (outside of 20% but would not lead to inappropriate treatment) following initial validation.

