- No more than 1 episode of inappropriate insulin dose resulting in severe hypoglycemia (glucose <55mg/dl) after initial sensor validation
- No more than 1 episodes of iatrogenic DKA (pH <7.3 or serum bicarbonate <15 mEq/L in the setting of elevated ketones) or hyperosmolar nonketotic state (osmolality \geq 320mOsm/kg with BG >600mg/dl and pH >7.3 or serum bicarbonate >15 mEq/L)
- No episodes of severe adverse events resulting in prolonged hospitalization, or other life-threatening complication that attributed to the study intervention
- No severe adverse events resulting in death, or other life-threatening complication that is attributed to the study intervention
- No severe adverse event resulting in prolonged hospitalization, or other life-threatening complication that attributed to the study intervention and is expected to recur

Oversight and monitoring. Study team oversight of nursing use of the CGM system will be performed through a combination of (1) daily evaluation of EHR and CGM Clarity data and (2) through rounding on CGM patients (mon-Friday by PI ([name]), Co-I ([name]) and/or study coordinator (to be named) (Saturday, Sunday and holidays by the MICU charge nurse who will communicate that day with study team members. Daily rounds will allow the study team to continuously evaluate protocol fidelity and identify any safety concerns. The study staff will evaluate CGM use daily through Clarity CGM and EHR data to determine the following:

3. Was initial validation criteria achieved correctly and at what frequency
4. Is ongoing validations performed Q4 hours and according to validation criteria
5. If validation is met did the nurse begin hybrid use with non-adjunctive CGM use
6. Using clarity reports study staff will assess the presence of alarms (e.g., <100mg/dl, >300mg/dl, predictive hypoglycemia) Alarms will be reviewed daily by research staff to ensure hypoglycemia and hyperglycemia are being treated in accordance with OSUWMC guidelines.
7. Those patterns of hyperglycemia or hypoglycemia assessed every 24 hours, will be reported to primary team via pager/direct message to allow changes to insulin dosing as needed (e.g., max drip rate for IV insulin titration).
8. Assessment of change in clinical status criteria (Table 1) in which per protocol the nurse would increase frequency of POC testing and validation.

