
IV. Regulatory and Safety Monitoring

A. OSU Center for Clinical and Translational Science Regulatory Oversight.

The OSU Center for Clinical and Translational Science (CCTS)-Regulatory Knowledge and Support Core assigned Data Safety Monitoring Board (DSMB) will oversee safety activity of the study. The DSMB will have expertise in either the scientific field of study, clinical trials, statistics, research ethics and/or epidemiology as is required of the study. The DSMB will review protocol-specific reports (Enrollment logs; device accountability logs; adverse event logs) created by the research team. These standard reports will include an overview of study objectives, a review of actual and projected accrual rates, an evaluation of patient demographics for balance of randomization, and a summary of the type, frequency, attribution, severity, seriousness and expectedness of adverse events. An interim

analysis of study results may be performed and source documents void of any identifiers, may be reviewed to allow the DSMB to independently judge whether the overall integrity and conduct of the protocol remain acceptable. The DSMB will make recommendations to the Principal Investigator that could include actions of continuation, modification, suspension, or termination.

In providing oversight for the conduct of this study, the DSMB will meet at a minimum of every 6 (six) months during the 2 (two) -year study to review all salient study information. Additional meetings may be scheduled as determined by the DSMB. The boundary for excess harm will equal an observed excess harm which in the judgment of the DSMB, is excessive. All serious adverse events regardless of severity, attribution and/or expectedness will be reported to the DSMB and the OSU Institutional Review Board(IRB) in accordance with their reporting guidelines. The DSMB recommended actions and all pertinent regulatory information will be forwarded to the Food and Drug Administration (FDA) appropriate Institutional Review Board(s), and Sponsor as appropriate.

B. Medical Device Accountability

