An investigator shall submit to the sponsor and to the reviewing IRB a report of any unanticipated adverse device effect occurring during an investigation as soon as possible, but in no event later than 10 working days after the investigator first learns of the effect (21 CFR 812.150(a)(1)). A sponsor who conducts an evaluation of an unanticipated adverse device effect under 812.46(b) shall report the results of such evaluation to the FDA and to all reviewing IRB's and participating investigators within 10 working days after the sponsor first receives notice of the effect. Thereafter the sponsor shall submit such additional reports concerning the effect as FDA requests (21 CFR 812.150(b)(1)).

E. Study and individual participant stopping criteria:

We plan to enroll participants in waves of 20 with ongoing analysis between waves. We plan to stop the study for the following conditions in consultation with the data safety monitoring board assigned to oversee safety activities and the study:

- Failure to meet initial validation criteria within 24 hours in 20% of participants
- CGM-meter pairs obtained during routine monitoring following initial validation without a change in clinical status prompting hourly monitoring meeting the following criteria:
 - Failure to detect clinically significant hypoglycemia (≥ 2 episodes): CGM value >100 mg/dl with no Urgent Low Soon alert while POC BG <70 mg/dl
 - Failure to detect severe hyperglycemia (≥ 2 episodes): CGM value <180 mg/dl when POC BG >400 mg/dl
 - Inappropriate treatment (≥ 2 episodes): CGM value triggers the opposite action than the POC BG value (CGM >180 mg/dl while POC BG <70 mg/dl or vice versa).
- ≥ 2 episodes of inappropriate insulin dose resulting in clinically significant hypoglycemia (glucose <55 mg/dl) after initial sensor validation
- ≥ 2 episodes of iatrogenic DKA (pH <7.3 or serum bicarbonate <15 mEq/L in the setting of elevated ketones) or hyperosmolar nonketotic state (osmolality ≥ 320 mOsm/kg with BG >600 mg/dl and pH >7.3 or serum bicarbonate >15 mEq/L)
- ≥ 2 episodes severe adverse events resulting in prolonged hospitalization, or other life-threatening complication that are attributed to the study intervention
- Any severe adverse event resulting in death, or other life-threatening complication that is attributed to the study intervention

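### A pilot with exactly 16 of 20 participants validated within 24 hours meets the continuation benchmark and, unless the stopping bullet is read as more than 20%, a study-stopping condition too

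*Combined protocol and SAP*

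**What the plan says.** Two lists in the combined protocol and SAP govern whether enrollment goes on.

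- **Section III.C, Staggered enrollment and initial pilot.** The first 20 patients form a pilot, with "benchmarks that must be met prior to subsequent enrollment". The first of the seven benchmarks is "Successful initial validation criteria within 24 hours in 80% of participants (16/20", so the plan itself prints the count.
- **Section IV.E, Study and individual participant stopping criteria.** "We plan to enroll participants in waves of 20 with ongoing analysis between waves". The study is to be stopped under the listed conditions "in consultation with the data safety monitoring board assigned to oversee safety activities and the study". The first condition is "Failure to meet initial validation criteria within 24 hours in 20% of participants". It states neither an inequality nor a denominator.

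Section IV.A adds that the DSMB's recommendations "could include actions of continuation, modification, suspension, or termination".

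**The concern.** The two bullets use the same criterion and the same 24-hour window, one counting successes and the other failures. Such a pair should divide the possible results cleanly, with every count on one side or the other. Here the count that the plan prints as good enough to continue is also the count at which the stopping bullet appears to begin.

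At stake is a go/stop decision at the end of the pilot. If 16/20 occurs, the study team and DSMB would have to decide what the bullet means after seeing the result. Pre-specified rules are meant to avoid that.

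**Working it through.** **Inputs.** The benchmark of 80%, printed as 16/20 (Section III.C); the stopping figure of 20% failing (Section IV.E); and the wave size of 20 (Sections III.A and IV.E). The documents give no expected 24-hour validation rate, so true rates *p* of 80, 85, 90 and 95% are assumed.

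**Step 1: reproduce the plan's figure.** 16/20 = 0.80, which agrees with the printed 80%.

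**Step 2: express it as failures.** 20 − 16 = 4, and 4/20 = 0.20, which is the figure in the stopping bullet.

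**Step 3: apply each reading of the stopping bullet to a pilot of 20.** The benchmark has no sign either; it is taken in its natural sense of at least 16.

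| Reading of *in 20%* | Stop at | Continue at | Both rules met at 16/20? |
|---|---|---|---|
| Exactly 20% | 4 failures | 4 or fewer failures | Yes |
| 20% or more | 4 or more failures | 4 or fewer failures | Yes |
| More than 20% | 5 or more failures | 4 or fewer failures | No; exact complements |

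**Step 4: see whether the rest of the plan settles the reading.** It does not.

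- Every event-count condition in Section IV.E that uses a number is inclusive (two or more episodes). By analogy that favors 20% or more.
- Some pairs across the two lists are exact complements. The benchmark "No more than 1 episode of inappropriate insulin dose resulting in severe hypoglycemia" faces a stopping condition of two or more such episodes, and the DKA/hyperosmolar pair works the same way. By analogy that favors more than 20%.
- Another pair is not complementary. The pilot benchmark is "No episodes of severe adverse events resulting in prolonged hospitalization", while the matching study-wide condition begins at two. So complementarity is not a drafting rule that can be relied on here.

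**Step 5: how often the boundary would be hit.** With independent participants,

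P(exactly 16 of 20) = C(20,16) × p^16 × (1 − p)^4, where C(20,16) = 4845.

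This equals P(at least 16) − P(at least 17):

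| Assumed true rate | P(at least 16) | P(at least 17) | P(exactly 16) |
|---|---|---|---|
| 80% | 0.630 | 0.411 | 0.218 |
| 85% | 0.830 | 0.648 | 0.182 |
| 90% | 0.957 | 0.867 | 0.090 |
| 95% | 0.997 | 0.984 | 0.013 |

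The last column is the chance that the missing sign matters at the pilot.

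**The case against.** The strongest reply is that the lists can be harmonized. Section III.C is the specific rule for the pilot and prints the count, while Section IV.E is the general list for the whole study. Reading the general bullet as more than 20% gives exact complements and removes the difficulty. In any case stopping is decided with the DSMB, so 16/20 would lead to a discussion and not to an automatic halt.

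Much of this stands. A reader might infer that the plan flatly contradicts itself, or that 16/20 would force the trial to stop. The documents support neither: one available reading removes the overlap, and the DSMB may recommend continuing. What the reply does not supply is text. Nothing says that the harmonizing reading applies or that the pilot list takes precedence, and the inclusive conditions in the same list point the other way. Consultation is also tied to the listed conditions, so it remains unclear whether 16/20 is one of them.

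A reader might also treat the unstated denominator, per wave or cumulative, as an equal fault. It has no bearing on the overlap, because the two counts are identical in the pilot. The conditions based on two or more episodes leave the same basis unstated.

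Nor should the point be sized by the chance of ever meeting the stop condition over later waves. At an assumed 85% rate, counted cumulatively over four between-wave looks, that chance is 0.262 under more than 20%. Of this, 0.170 comes from pilots with five or more failures, which miss the benchmark on any reading.

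**Conclusion.** The concern holds as a minor ambiguity. At 16/20, a count the plan itself names, the continuation benchmark is met, and so is the stopping condition unless that bullet means more than 20%.

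The chance of landing there is about 22, 18, 9 and 1% at assumed true rates of 80, 85, 90 and 95%. It is therefore appreciable if true validation is between 80 and 90% and negligible near 95%. These figures rest on assumed rates and on independence between participants; the textual overlap rests on neither. Validation is one of seven pilot benchmarks, the DSMB is consulted before any stop, and the glycemic comparison and power calculation are untouched.

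**What to change.** Before enrollment, reconcile Sections III.C and IV.E. Add an explicit inequality to the validation bullet in Section IV.E so that it is the exact complement of the Section III.C benchmark and 16/20 falls on one side only. Which side is for the sponsor and DSMB to choose; if 16/20 is to count as stopping, the printed benchmark count must change to match. As a side note, the same edit can say whether the 20% is counted per wave or cumulatively after the pilot.

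The cost is one sign in one bullet, any matching change to the benchmark, and the DSMB's agreement. Sample size, data collection and analysis do not change.

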The Android phone, which will receive glucose data from the CGM transmitter, will be kept outside of the patient room allowing the staff nurse to visualize discrete values, trends and hear alarms without entering the patient's room. OSUWMC MICU employs a staffing ratio maximum of 1 nurse for 2 patients. MICU staff nurses will only care for 1 patient using CGM at a time. Alarms are visually displayed and audible from both the dashboard and receiver (Android phone); however nurses are instructed to confirm all glucose values and the presence of alarms on the receiver devices at the bedside prior to treatment. All nurses in the MICU are trained on CGM alarm recognition and response. In a previous analysis, nurses reported alarms were audible throughout the MICU unit.² If the nurse assigned to the CGM patient participant is not immediately available when an alarm is sounding, another nurse or the charge nurse is expected to respond to the alarm and provide appropriate treatment. This same alarm response delegation is employed for other MICU systems including cardiac telemetry, Pulse oximetry, and ventilator alerts. Nurses will follow standard approved OSUWMC guidelines, policies and provider dosing orders for treatment of hyperglycemia and hypoglycemic events. Episodes of hypoglycemia and hyperglycemia will be responded to in real time by nursing staff. Our hypoglycemia guideline (Table 3) treats glucose <80mg/dl with Dextrose D50% for critically ill patients. Dosing is stratified based on degree of hypoglycemia with follow-up required within 15 minutes. For hypoglycemia <60mg/dl nurses are instructed to inform the provider via pager/direct chat. Nurses in the MICU are experienced in administration dextrose D50% using the described hypoglycemia protocol. If the patient is ordered to undergo magnetic resonance imaging (MRI), computerized tomography (CT) radiographic procedures, or diathermy than the sensor/transmitter will be removed prior to the procedure as these procedures could potentially interfere with sensor accuracy.²⁹ A new sensor will be inserted after procedure is completed and will undergo initial validation prior to use.

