The patient will remain on CGM for the duration of their hospital stay and if discharged to home may transition to personal use of the Dexcom G6. The Dexcom G6 sensor is replaced every 10 days and will be removed and then replaced for some radiographic procedures or sensor failure. CGM data is automatically transferred to Dexcom's cloud-based Clarity system.

Table 3. OSUWMC Hypoglycemia Guideline, Patients Who are Not Alert, Are NPO, or on IV Insulin Infusion

Blood Glucose (BG) Level*	Action	Follow-Up
60-79 mg/dL	
 • Administer 7.5 g Dextrose D50% (15 ml) IV* • Consider calling House Officer if patient experiencing recurrent BG <70 mg/dL in past 12 h 	
 • Recheck BG q 15 min following treatment and treat accordingly until ≥ 80mg/dl • Once ≥ 80mg/dl, recheck BG q1h x2 (x4 if <45mg/dL at onset), then resume POC glucose as previously ordered, Patients who are admitted with hypoglycemia should be monitored at least q 4h for a minimum of 24h
45-59 mg/dL	
 • Administer 12.5 g Dextrose D50% (15 ml) IV* • Call House Officer to report BG and action taken 	
<45 mg/dL	
 • Administer 25 g Dextrose D50% (15 ml) IV* • Call House Officer to report BG and action taken 	
ALL	
 • Consider adding Dextrose 5% to maintenance IV fluids at a rate of ≥ 50ml/hr or increase rate of existing maintenance IV if dextrose source already present 	
 • If > 4h from initial event and BG ≥ 80mg/dl for two consecutive readings, may consider reducing IV dextrose

Variables and measures. *Clinical utility criteria:* Time to CGM validation within hybrid protocol parameters, mean percent of dosing decisions determined by CGM, changes in insulin dosing from standard guideline or outside standard times in response to alarm and/or trend data (as measured by manufacturer download data and corresponding EHR documentation). *Fidelity criteria:* Proportion of times CGM used non-adjunctively/number of

times non-adjunctive use indicated per protocol. *Adoption criteria:* Proportion of patients approached to received CGM monitoring/number of patients eligible to receive initial CGM monitoring.

RQ 2: To assess the degree to which CGM implementation within the ICU environment effects nursing workload and care delivery.

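### In the hypoglycemia guideline (Table 3), the printed 15 ml of D50% holds 7.5 g of dextrose, not the 12.5 g and 25 g ordered in the two most severe rows

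*Combined protocol and SAP*

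**What the plan says.** Table 3 (OSUWMC Hypoglycemia Guideline, in section III.C under RQ 1) covers patients who are not alert, are NPO, or are on an IV insulin infusion. It gives one dextrose dose per glucose tier:

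- 60-79 mg/dL: "Administer 7.5 g Dextrose D50% (15 ml) IV"
- 45-59 mg/dL: "Administer 12.5 g Dextrose D50% (15 ml) IV"
- below 45 mg/dL: "Administer 25 g Dextrose D50% (15 ml) IV"

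The RQ 1 Procedures text presents this table as the guideline in use: "Our hypoglycemia guideline (Table 3) treats glucose <80mg/dl with Dextrose D50% for critically ill patients". It then states: "Dosing is stratified based on degree of hypoglycemia with follow-up required within 15 minutes". The same paragraph says: "Nurses will follow standard approved OSUWMC guidelines, policies and provider dosing orders for treatment of hyperglycemia and hypoglycemic events".

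The follow-up column says "Recheck BG q 15 min following treatment and treat accordingly until" glucose reaches at least 80 mg/dl. Both lower tiers also carry the instruction "Call House Officer to report BG and action taken".

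**The concern.** The dose in grams rises across the three tiers, but the volume of the same solution stays at 15 ml. One fixed volume of one concentration cannot deliver three different doses, so at least two rows contradict themselves. They are the two rows for the most severe episodes.

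What is at stake is patient safety in this trial's own population. IV insulin is one of the two routes into the study, and patients on an insulin infusion are among those Table 3 covers. Table 1 also refers nurses to the institutional hypoglycemia policy when a CGM or POC glucose falls below 70 mg/dl. Every glucose below 55 mg/dl falls in one of the two inconsistent rows, and that is the level used in the pilot benchmark and in a study stopping criterion. Those rules do not use the dextrose volume, so they are not altered. The patients they are meant to protect are nevertheless the ones these rows treat.

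A nurse who drew up the printed volume would underdose the first rescue treatment, most of all in the most severe tier.

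**Working it through.** **Inputs, all from Table 3.** Grams ordered: 7.5, 12.5 and 25. Volume printed: 15 ml in every row. Solution: D50% in every row.

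**Concentration.** D50% is 50 g per 100 ml, which is 50 / 100 = 0.5 g/ml. The 60-79 mg/dL row gives the same figure: 7.5 g / 15 ml = 0.5 g/ml. That row is reproduced exactly and needs no change.

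**Formulas.**
- Volume needed = grams / 0.5
- Grams in the printed volume = 15 × 0.5 = 7.5 g
- Share delivered = 7.5 / grams ordered
- Shortfall = grams ordered − 7.5

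| Tier (mg/dL) | Ordered | Printed volume | Volume needed | Share in 15 ml | Shortfall |
|---|---|---|---|---|---|
| 60-79 | 7.5 g | 15 ml | 7.5 / 0.5 = 15 ml | 7.5 / 7.5 = 100% | 0 |
| 45-59 | 12.5 g | 15 ml | 12.5 / 0.5 = 25 ml | 7.5 / 12.5 = 60% | 5 g (10 ml) |
| below 45 | 25 g | 15 ml | 25 / 0.5 = 50 ml | 7.5 / 25 = 30% | 17.5 g (35 ml) |

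**Could another concentration reconcile the rows?** Fitting 12.5 g into 15 ml needs 12.5 / 15 = 83% w/v. Fitting 25 g into 15 ml needs 25 / 15 = 167% w/v. Neither is D50%, which is the solution named in both rows.

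**Which figure is likelier to be wrong?** If the volumes were right, all three tiers would receive 7.5 g and there would be no stratification. The RQ 1 Procedures text says that dosing is stratified by severity. The grams fit that statement and the volumes do not. The likeliest explanation is that the 15 ml from the first row was repeated in the other two. The protocol does not say which figure governs, and no other section restates or corrects the volumes.

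**The case against.** The strongest reply is that Table 3 reproduces existing institutional care and is not the study intervention. Nurses follow the approved guidelines and provider orders, and the protocol describes them as experienced in giving D50% under this guideline. The governing policy is outside the document and may be correct, so the slip may exist only in this copy. Harm then needs a nurse to use this copy, to follow the volume rather than the grams printed before it, and to overlook that three rising doses share one volume. Even then, glucose is rechecked every 15 minutes and treated again, the House Officer is called in both affected tiers, and added dextrose 5% in maintenance fluids is to be considered at every tier.

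This stands as a limit on the likely harm. It does not make the table right. The recheck acts after the first dose has been given. The protocol's Nurse training paragraph also says the study protocol and training materials are kept at the bedside of every participant. That may mean only the CGM + POC procedure, so it does not prove that Table 3 is there, but it makes that a realistic possibility.

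Two textual points were also weighed. Each dose line ends in an asterisk, and no matching footnote appears in the text as read. The asterisk is also on the consistent row and on the glucose column header, and no footnote could make 25 g fit in 15 ml of D50%. A fault in reading the table from PDF cannot be wholly excluded, but the three cells are intact and the grams vary as expected. Checking the source page would settle it.

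**Conclusion.** The concern holds. In the 45-59 mg/dL and below 45 mg/dL rows of Table 3, grams and volume contradict each other, and the volumes are the likelier error. If the grams are correct and the printed volume is followed, the first dose is 60% of intended (5 g short) and 30% of intended (17.5 g short), respectively. These figures describe a single dose, not total treatment.

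The contradiction itself rests only on D50% being 0.5 g/ml, which the first row confirms. The direction of the error rests on the statement that dosing is stratified. Whether any copy in clinical use carries the wrong volumes cannot be settled from the document. The point should be fixed because it concerns a rescue drug dose, but it has no bearing on design, sample size, power or analysis.

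**What to change.** Check the two rows against the approved institutional guideline with pharmacy. If the grams are confirmed, change the volume to 25 ml for 12.5 g (45-59 mg/dL) and to 50 ml for 25 g (below 45 mg/dL), and leave the 60-79 mg/dL row as it is. At the same time, supply or remove the footnote that the asterisks point to. If the table has been circulated in training material or placed at the bedside, replace those copies and notify staff.

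The cost is two table cells, a pharmacy check and possibly a staff notice.
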